11.2. Secondary Objective

Secondary Objective #1

Evaluate the impact of the intervention on whether SND subjects undergo an IPG implant

Hypothesis

The secondary objective will be tested with the following hypothesis:

$$H_0: p_{1t} = p_{2t}$$

$$H_A: p_{1t} \neq p_{2t}$$

where p_{1t} is the proportion of patients with an IPG in Phase I and p_{2t} is the proportion of patients with an IPG in Phase II at time point t .

Endpoint Definition

The absolute change in the proportion of SND subjects receiving indicated therapy at pre-specified time points (% = number receiving IPG/number with SND diagnosis x 100 at time point t where $t = 3, 6, \text{ and any additional 3-month interval for which there is sufficient follow-up information}$) and the absolute change in the number of subjects implanted per person-year.

Analysis Methods

A. Statistical Methodology

To compare the proportion of SND subjects that receive indicated therapy pre-intervention (Phase I) to the proportion post-intervention (Phase II), a binomial exact test will determine statistical significance. The proportion of subjects diagnosed will be evaluated at multiple time points because the time from diagnosis to implant is expected to vary by site. Shorter time intervals will be used to evaluate the proportion of implants than for the proportion of diagnosis because implants typically occur more quickly than the SND diagnosis. Thus, times are pre-specified starting at 3 months and any additional 3-month interval thereafter for which there is sufficient follow-up data available to compare study phases. Proportions calculated at all available time points will be reported. Additionally, a Poisson regression will compare the average number of subjects with an implant where the subject time in study beginning at the time of SND diagnosis is treated as an offset in the model. The above described tests will be performed separately within geography/country as well as overall. Further, similar tests will compare the differences in the types of therapy received in Phase I and Phase II. For example, a binomial exact test will compare the frequency of dual chamber device use pre- and post-intervention.

B. Determination of Patients/Data for Analysis

The number of subjects that meet inclusion criteria and obtain an SND diagnosis shall be included in this analysis. The proportion estimates will be calculated based on information from fixed time points at 3 months of follow-up, 6 months of follow-up, and any additional 3-month interval thereafter for which there is sufficient follow-up data available to compare study phases. The number of subjects that obtain an IPG by pre-specified time point $t = 3, 6, \text{ etc.}$, will be included in the numerator and the number of subjects with an SND diagnosis will be included in the denominator.

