4. METHODOLOGY

The Brady MX study is a prospective, sequential, post market study with an educational phase and any market released pacemaker from the Medtronic family of devices may be used in this study. It is hypothesized that the use of a practice-specific process improvement intervention consisting of education, diagnostic algorithm(s) and

documentation tools that advocate and reinforce adherence to consensus treatment guidelines will improve the quality of care for patients with sinus node dysfunction (SND). The study will be conducted in two phases, with Phase I serving as control subjects and Phase II measuring the impact of the intervention.

The study will be conducted in compliance with the Clinical Investigation Plan, Clinical Trial Agreement, approved labeling, latest version of the Declaration of Helsinki, and laws and regulations of the country in which the study is conducted, including data protection laws.

Principles of the Declaration of Helsinki have been incorporated into this study by means of the patient informed consent/Patient Data Release process, IRB/MEC approval (if required); study training, clinical trial registration, risk benefit assessment, and publication policy, etc.

The study may enroll up to 500 Mexican subjects. with at least 210 subjects enrolled per study phase. Once enrolled, Phase I subjects should be followed for approximately 6 months and Phase II subjects should be followed for approximately 6 months. Brady MX is anticipated to be completed in mid-2018.

Subject data will be collected at enrollment/baseline, diagnostic assessment visits and implant visit. Data will continue to be collected until one of the exit criteria has been met. Brady MX does not mandate specific requirements regarding any other procedures, subject visits to the clinic, clinical treatment of subjects or device programming. Clinical data will be collected using electronic case report forms.

Centers will be eligible to enroll subjects in Brady MX upon Medtronic's receipt of required center activation materials and written approval.

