5.4. Diagnostic Assessment Visit(s)

A diagnostic assessment is any post enrollment visit to the study center for continued diagnostic assessment or management. During these visits information about utilization of diagnostic tests, results and cardiovascular medication use will be collected. Information about the final diagnosis and treatment decision will also be collected during the diagnostic assessment visit. The diagnostic assessment visit data will be complete:

- When the subject meets study exit criteria
- 6 months after the last Phase I enrollment for Phase I subjects
- 6 months after the last Phase II enrollment for Phase II subjects
- Patient education tools have been reviewed with the patient by the investigator (Phase II only)

The study protocol does not dictate when the Diagnostic Assessment(s) is/are to occur.

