5.6. Study Exit

Subjects may be exited from the study for any of the following situations, including but not limited to:

- Subject does not meet an indication for pacing therapy
- Subject meets an indication for pacing but not a SND indication for pacing therapy

- Subject has met a SND indication for pacing therapy but will not be receiving pacing therapy
- Subject diagnosis meets an SND indication for IPG Therapy and a non-Medtronic/Vitatron device was implanted.
- Completion of study follow-up with no diagnosis made
- Study Closure
- Subject lost to follow-up, patient doesn't come back after baseline for diagnosis test decision
- Subject death
- Subject did not meet inclusion/exclusion criteria
- Subject chooses to withdraw (e.g., consent withdrawal, relocation to another geographic location)
- Investigator deems withdrawal necessary (e.g., medically justified, failure of subject to maintain adequate study compliance)

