5.7. Subject Follow-up after Withdrawal

Upon withdrawal from the study, no further study data will be collected or study visits will occur for the subject.

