To compare the proportion of SND subjects that receive a referral for indicated therapy pre-intervention (Phase I) to the proportion post-intervention (Phase II), a binomial exact test will determine statistical significance. The proportion of subjects diagnosed will be evaluated at multiple time points because the time from diagnosis to implant is expected to vary by hospital. Shorter time intervals will be used to evaluate the proportion of referrals than for the proportion of diagnosis because implants typically occur more quickly than the SND diagnosis. Thus, times are pre specified starting at 3 months and any additional 3-month interval thereafter for which there is sufficient follow-up data available to compare study phases. Proportions calculated at all available time points will be reported. Additionally, a Poisson regression will compare the average number of subjects with an implant where the subject time in study beginning at the time of SND diagnosis is treated as an offset in the model.

Determination of Patients/Data for Analysis

The number of subjects that meet inclusion criteria and obtain an SND diagnosis shall be included in this analysis. The proportion estimates will be calculated based on information from fixed time points at 3 months of follow-up, 6 months of follow-up, and any additional 3-month interval thereafter for which there is sufficient follow-up data available to compare study phases. The number of subjects that obtain an IPG referral by pre-specified time point $t = 3, 6, \text{ etc.}$, will be included in the numerator and the number of subjects with an SND diagnosis will be included in the denominator.

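### Implants per person-year are compared on person-time that can stop at a decision against pacing, which pulls the rate ratio towards 1 by an amount set by site exit practice

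*Combined protocol and SAP*

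**What the plan says.** Primary Objective #2 (section 11.1) and the secondary objective (section 11.2) each have a two-part endpoint: a change in a proportion among SND-diagnosed subjects, and "the absolute change in the number of subjects implanted per person-year". For the second part, section 11.1 reads, in a quotation cut short here: "a Poisson regression will compare the average number of subjects with an implant where the subject time in study beginning at the time of SND". Section 11.2 uses the same model and shows how the sentence ends: "subject time in study beginning at the time of SND diagnosis is treated as an offset in the model". Neither section says when that time ends.

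Time in study is governed elsewhere:

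- Section 4: "Data will continue to be collected until one of the exit criteria has been met".
- Section 5.6: "Subjects may be exited from the study for any of the following situations, including but not limited to". One listed situation is "Subject has met a SND indication for pacing therapy but will not be receiving pacing therapy". Receipt of a sponsor device is not listed.
- Section 5.4: "Information about the final diagnosis and treatment decision will also be collected during the diagnostic assessment visit". Table 1 in section 5.2 puts final diagnosis, device indication and treatment decision in the same visit column.

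The null hypotheses of both objectives are written in proportions. The binomial exact test decides significance, and the Poisson model is additional.

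**The concern.** A rate needs person-time that does not depend on whether the event happens. Here a subject who fails the endpoint, being indicated but not paced, can leave the denominator because of that failure. A subject who is implanted or still waiting stays in it. If non-recipients contribute little time, nearly all person-time comes from recipients. The rate then mostly reflects how long recipients are observed per implant, and says little about the share of indicated subjects who are implanted.

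At stake is a rate named in the endpoint definitions of one primary and one secondary objective. Its value would vary with how promptly each site completes exit paperwork.

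**Working it through.** **The plan's own figures.** The plan gives no rate, power or sample size for implants per person-year. Its only sample-size statement is for Primary Objective #1: 10% versus 20%, 200 per phase, type I error 0.05, power 0.80. The two-sided pooled z formula gives (1.96 × √0.255 + 0.8416 × √0.25)² / 0.10² = 199, so the 200 reproduces. It implies about 20 SND subjects in Phase I and 40 in Phase II. These counts cancel from the rate ratio below.

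**Inputs.** From the plan: offset starting at diagnosis, optional exit at a decision against pacing, two phases. Assumed, because the documents give no value: uptake p = 40% versus 80%; mean time of implanted subjects w = 2 months in both phases, with time stopped at implant; mean time d of non-recipients, varied from 0 to 6 months.

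**Formula.** Rate per person-year = 12 × p / (p × w + (1 − p) × d), times in months.

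| Non-recipients' time | d | Phase I rate | Phase II rate | Ratio |
|---|---|---|---|---|
| Exit on day 0 | 0 | 12 × 0.4/0.80 = 6.00 | 12 × 0.8/1.60 = 6.00 | 1.00 |
| Exit at 0.1 month | 0.1 | 12 × 0.4/0.86 = 5.58 | 12 × 0.8/1.62 = 5.93 | 1.06 |
| Exit at 0.5 month | 0.5 | 12 × 0.4/1.10 = 4.36 | 12 × 0.8/1.70 = 5.65 | 1.29 |
| 30% pending 6 months, rest exit at 0.1 month | 0.3 × 6 + 0.7 × 0.1 = 1.87 | 12 × 0.4/1.922 = 2.50 | 12 × 0.8/1.974 = 4.86 | 1.95 |
| All contribute 6 months | 6 | 12 × 0.4/4.40 = 1.09 | 12 × 0.8/2.80 = 3.43 | 3.14 |

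Uptake is the same in every row. Only the exit practice changes.

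**If time runs on after implant.** The plan does not say that time stops at implant, so a second case was run: uptake 50% versus 80%, with implanted subjects contributing w = 6 months. At d = 0.5 the rates are 12 × 0.5/3.25 = 1.85 and 12 × 0.8/4.90 = 1.96, ratio 1.06. At d = 0, 0.1 and 1 month the ratios are 1.00, 1.01 and 1.12. Only at d = 6 does the ratio equal the uptake ratio: 1.00 versus 1.60, ratio 1.60.

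**Simulation of that case** (4,000 runs, 20 versus 40 SND subjects, implanted subjects kept to phase end). With d from about 1 day to 1 month, the rate ratio is 1.00 to 1.11 and the Poisson test rejects in essentially no run. Fisher's exact test on the proportions has power of about 0.62 in the same data.

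**The case against.** Several points on the other side stand.

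- **Exit is optional and its timing is unknown.** Section 5.6 says that subjects may be exited. Section 5.4 allows several assessments and does not fix their timing. Sharing a visit type does not mean that diagnosis and decision fall on the same day. A reader might infer that the rate cannot register higher uptake at all. That is exact only if every non-recipient leaves on day 0; with 30% pending the ratio is already 1.95.
- **The formal tests are elsewhere.** A reader might infer that the study could miss a doubling of acceptance. The documents do not support this: the hypotheses are tested on proportions whose denominator is all SND-diagnosed subjects, decliners included.
- **A reversed effect** needs a further assumption. With a 3-month wait in Phase II only, the ratio is 0.71 at d = 0.1 and 2.44 at d = 6, but nothing in the plan suggests a longer Phase II wait.
- **Section 5.7** might be read as closing data capture at every exit. Its text is "Upon withdrawal from the study, no further study data will be collected or study visits will occur for the subject", and section 5.6 lists withdrawal separately from a decision against pacing. The point rests on sections 4 and 5.6 instead.
- **Device brand.** The exit item for other manufacturers' devices might suggest a brand-dependent rate. That exit follows the event, and the difference vanishes if time stops at implant.
- **Zero offsets.** An undefined log(0) for day-0 exits arises only in a subject-level fit; totals by phase avoid it.

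What remains is that no rule keeps non-recipients in the person-time or says when it ends.

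**Conclusion.** The point holds for the per-person-year comparison in Primary Objective #2 and the secondary objective. As written, person-time depends on the treatment decision. With equal waits in both phases and early exit of non-recipients, the rate ratio is attenuated towards 1. Under 40% versus 80% uptake and a 2-month wait, the same effect can appear as anything from 1.00 to 3.14, depending on exit practice alone. Uptake, wait and exit times are all assumptions, so the direction is firmer than the size. The binomial comparisons are largely unaffected; what they can miss is a subject who accepts therapy after having been exited.

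**What to change.** In section 11.1 (Objective #2) and section 11.2, replace time in study as the offset with time from SND diagnosis to the earliest of implant, death, consent withdrawal, loss to follow-up, or a fixed cut-off that is the same in both phases, for example 6 months after diagnosis. State that a decision against pacing, or an exit for that reason, does not end person-time. Such subjects count as without the event up to the cut-off, as they already do in the proportions. Say also how subjects diagnosed too late in a phase to reach the cut-off are handled, again without regard to the treatment decision.

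The cost is analysis wording: no added visit, no change to treatment, and no change to section 5.6. The downside is that a change of mind after exit is missed, as it already is in the proportions. Chart capture to the cut-off would close that gap but is optional. It would require changing section 5.6 and having the revised plan approved at up to 10 sites.

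The change corrects what is estimated and does not guarantee power. With 50% versus 80% uptake, 20 versus 40 SND subjects, and all of them kept to phase end, simulated Poisson power was only about 0.13. The proportions should therefore remain the main comparison.

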1.2. Study Scope

The study may be conducted in up to 10 sites under oversight by the “Secretaria de Salud” in Mexico. The study will be conducted in two phases, with Phase I serving as control subjects and Phase II measuring the impact of the intervention. Up to 500 subjects will be enrolled in the study with at least 210 enrolled per phase. An enrollment target of 45 subjects per center in total is desired to make center-specific outcomes more meaningful and reliable in measuring changes in diagnostic rates and patient acceptance of indicated therapy. Centers that enroll faster than others will be allowed to enroll up to 42 subjects within each phase of the study.

All study subjects will be followed until the study exit criteria are met or until official study closure. Study closure is defined as closure of a clinical study that occurs when Medtronic and/or regulatory requirements have been satisfied per the Clinical Investigation Plan and/or by a decision by Medtronic or regulatory authority, whichever occurs first. The expected study duration from first enrollment to last follow-up, is approximately 26 months.

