The aim of Brady MX is to improve adoption of consensus treatment guidelines in Mexico for SND indicated patients as described in the ACC/AHA/HRS guidelines² and ESC guidelines³. Implantable Pulse Generator (IPG) therapy has been integrated into the ACC/AHA/HRS guidelines and ESC guidelines without evidence from large randomized clinical trials (RCT). While the RCT is considered the gold standard for establishing that a therapy causes a clinical outcome effect, the scientific community is calling for clinical research beyond the RCT. A manuscript in Circulation in 2008¹² states that the external validity of RCTs must be supplemented by real world “effectiveness research”, including pragmatic studies, meta-analyses and observational trials. Guidelines and major publications help with awareness of what is possible when treating disease and an important component of adoption is the physician’s personal experience with the therapy. As such, the evidence in this study will provide personal experience, powerful information for the individual physician, and an aggregated analysis.

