4.4. Minimization of Bias

Potential sources of bias in this study may result from the Hawthorne effect, selection of study centers, selection of subjects, treatment of subjects, and evaluation of study data. The following methods have been incorporated into the study to minimize potential bias.

- Center selection criteria, documented under separate cover, will need to be met prior to participation in Brady MX. Study center characteristics will be collected at activation on possible differences that may affect the primary endpoints. Centers will be used as their own control
- Subjects will be screened to confirm eligibility with the help of screening logs, for enrollment with defined inclusion/exclusion criteria prior to enrollment
- Subject demographics will be collected at baseline on possible differences that may affect the primary endpoints
- It is anticipated that the distribution of subjects with various co-morbidities will vary by study centers. To minimize potential bias, all sites will be encouraged to enroll at least 5 subjects in each study Phase and enrollment at a site cannot exceed 42 subjects per phase to ensure a more even distribution of data
- All study Clinicians will be required to follow the Clinical Investigation Plan
- All study clinicians and Medtronic personnel will be trained on their respective aspects of the clinical investigation plan using standardized training materials.

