11.1. Primary Objective(s)

Primary Objective #1

Evaluate the impact of the intervention on the diagnosis of SND.

Hypothesis

The primary objective will be tested with the following hypothesis:

$$H_0: p_{1t} = p_{2t}$$

$$H_A: p_{1t} \neq p_{2t}$$

where p_{1t} is the proportion of patients with SND in Phase I and p_{2t} is the proportion of patients with SND in Phase II at time point t .

Endpoint Definition

The absolute change in the proportion of subjects diagnosed with SND at pre-specified time points ($\% = \text{number diagnosed} / \text{number enrolled} \times 100$ at time point $t = 6$, or t is a multiple of 6 representing any additional 6-month interval for which there is sufficient follow-up information) and the absolute change in the number of subjects diagnosed with SND per person-year.

Analysis Methods

A. Statistical Methodology

To compare the proportion of subjects with an SND diagnosis pre-intervention (Phase I) to the proportion post-intervention (Phase II), a binomial exact test will determine statistical significance. The proportion of subjects diagnosed will be evaluated at multiple time points because the time to diagnosis is expected to vary by hospital. Thus, times are pre-specified starting at 6 months and any additional 6-month interval thereafter for which there is sufficient follow-up data available to compare study phases. Proportions calculated at all available time points will be reported. Additionally a Poisson regression will compare the average number of subjects with an SND diagnosis in Phase I and Phase II where the subject time in study is treated as an offset in the model. The above described tests will be performed separately within site as well as overall.

B. Determination of Patients/Data for Analysis

All subjects that are enrolled in the study and that meet study inclusion/exclusion criteria will be included in the determination of the proportion estimates. The proportion estimates will be calculated based on information from fixed time points at 6 months of follow-up, and any additional 6-month interval thereafter for which there is sufficient follow-up data available to compare study phases. The number of subjects that obtain a SND diagnosis by pre-specified time point t is included in the numerator and the number of subjects enrolled is included in the denominator.

Sample Size Methods and Assumptions

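### The by-country repeat of the implant tests has only one level, and no site-level or site-stratified comparison of implants is planned

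*Combined protocol and SAP*

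**What the plan says.** Section 11.2, Statistical Methodology, sets out an exact test of the implant proportion among SND subjects and a Poisson regression with time since SND diagnosis as offset. It then adds: "The above described tests will be performed separately within geography/country as well as overall".

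The study has one country. Section 4 states: "The study may enroll up to 500 Mexican subjects". Section 2 states: "The aim of Brady MX is to improve adoption of consensus treatment guidelines in Mexico for SND indicated patients". Section 1.2 states: "The study may be conducted in up to 10 sites", under the oversight of the Mexican health ministry.

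Three other places bear on the choice of stratum:

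- Section 11.1, Primary Objective #1, uses the same sentence form with a different unit: "The above described tests will be performed separately within site as well as overall".
- Section 4.4 lists among its measures against bias: "Centers will be used as their own control".
- Section 1.2 sets a per-center enrollment target to make "center-specific outcomes more meaningful and reliable in measuring changes in diagnostic rates and patient acceptance of indicated therapy".

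Primary Objective #2 (referral for an IPG) names no break-out, although its Poisson model also counts implants.

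**The concern.** A break-out with one level adds no information: the within-country test has the same counts, person-time and p-value as the overall test. The unit that does vary, the site, is not used for implants.

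This matters because the study compares two consecutive periods without a concurrent control. Comparing each center with itself is one of the few protections such a design has. The pooled comparison in 11.2 does not use it. The denominator is subjects diagnosed with SND, a number the intervention is meant to raise, and the rise may differ between centers. If centers with different implant rates supply different shares of that denominator in the two phases, the pooled proportion can move with no change at any center. Nothing in the planned implant output would show it.

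**Working it through.** **1. The plan's own figure.** The documents give no sample size for the implant objective. For Primary Objective #1 they state 200 per phase for 10% versus 20% at two-sided 0.05 and 80% power. The pooled normal approximation gives 199 per phase (power 80.2% at 200), so the figure reproduces by that method; 200 × 1.05 = 210 is the stated enrollment minimum. The point here does not depend on that calculation. It only uses the rates.

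**2. Levels of the planned stratum.** Number of countries = 1. The within-country 2×2 table is the overall 2×2 table, and the person-time is the same, so both the exact test and the Poisson comparison are duplicated. Planned comparisons of implants by site or stratified by site: none. In section 11.3 the only by-site analysis concerns enrollment out of those screened.

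**3. Expected SND subjects at the plan's rates.**

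| | Phase I (10%) | Phase II (20%) |
|---|---|---|
| All sites, 210 per phase | 210 × 0.10 = 21 | 210 × 0.20 = 42 |
| Per site, 10 equal sites (21 each) | 2.1 | 4.2 |
| Per site, 5 sites at the cap of 42 | 4.2 | 8.4 |

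**4. What a change in center mix can do (assumed rates; the documents give none).** Let half the centers implant 30% of SND subjects and half 70%, in both phases.

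- Phase I, equal shares: 0.5 × 0.30 + 0.5 × 0.70 = 0.50.
- Phase II, high-rate share 70%: 0.3 × 0.30 + 0.7 × 0.70 = 0.58.
- Artefact = gap in rates × change in share = 0.40 × 0.20 = 0.08.
- Standard error of the difference = √(0.50 × 0.50/21 + 0.58 × 0.42/42) = √(0.0119 + 0.0058) = 0.133.
- Ratio = 0.08/0.133 = 0.6.

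Range: with half the gap in rates, the artefact is 0.20 × 0.20 = 0.04, about 0.3 standard errors. With the share moving the other way, to 30%, the pooled figure falls to 0.7 × 0.30 + 0.3 × 0.70 = 0.42. With no change in share, it is zero.

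The enrollment rules do not exclude such a shift. A site is encouraged to enroll at least 5 per phase and may enroll up to 42, that is 5/210 = 2% to 42/210 = 20% of a phase. If enrollment followed the same shares, 70% of 210 is 147 subjects, or about 29 at each of five sites, which is under the cap.

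**5. Whether separate per-site tests would help.**

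- 2 versus 4 SND subjects: the most extreme table has Fisher two-sided p = 1/15 = 0.067, so 0.05 cannot be reached.
- 4 versus 8: the most extreme table has p = 1/495 = 0.002, so 0.05 can be reached. Exact power is still only about 1% to 7% under assumed implant proportions of 30% vs 50%, 40% vs 70%, 50% vs 80% and 20% vs 60%.

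**6. Cost of stratifying.** A site with n₁ and n₂ SND subjects has Mantel-Haenszel weight n₁n₂/(n₁ + n₂), which is zero if either count is zero. With 21 enrolled per site per phase and the plan's rates at every site, the chance of no SND subject is 0.9²¹ = 0.11 in Phase I and 0.8²¹ = 0.01 in Phase II. That is 1 − 0.89 × 0.99 = 0.12, or about 1 site in 10 dropping out.

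**The case against.** The strongest reply is that this is leftover wording with no wrong result attached. The design figure title in section 4.3 and the benefits statement in section 9.1 carry a different study name, so a by-country phrase from elsewhere is plausible. A duplicated test gives no wrong estimate or p-value. That stands, and it is why the point is minor. But correcting the word alone would leave either nothing at site level or the near-powerless tests of step 5.

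A reader might infer that the plan promises a center-level implant test and then breaks the promise. The documents do not say so. The own-control statement is partly met because the same centers supply both phases. The enrollment target in section 1.2 speaks of acceptance of therapy, which fits the receive-or-decline decision of Ancillary Objective #1 at least as well as implant receipt. Section 11.2 mentions variation by site in time to implant as the reason for several time points, not for a site analysis. Still, no section analyses implants by site in any form.

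A reader might also take the move from 50% to 58% as an expected bias. It is one assumed scenario, too small at these counts to drive the result alone. Nor is the 0.067 floor general: it needs 10 equal sites, and the plan says up to 10.

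Finally, geography could mean regions within Mexico. No regions are defined, and section 5 uses the same paired term for local documentation requirements. Regional strata would not be a within-center comparison in any case.

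**Conclusion.** The point holds. The country break-out in 11.2 is empty, and the implant comparison is planned only in pooled form, so a change in center mix between phases would go unseen. Primary Objective #2 has the same gap, since it names no break-out. How far this could move the implant proportion cannot be derived from the documents: the assumed cases above run from 0 to 8 points in either direction, up to about 0.6 standard errors at 21 versus 42 SND subjects. Those counts assume 210 per phase and the plan's 10% and 20% diagnosis rates. The documents do not support a claim that the implant result will be biased or that a stated commitment is breached. The severity is low: a clear improvement to a secondary analysis at little cost.

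**What to change.** In section 11.2, Statistical Methodology, replace the by-country sentence with wording such as: implants and SND diagnoses will be tabulated by site and phase, without separate per-site tests; in addition, one site-stratified phase comparison (a Mantel-Haenszel risk difference with a stratified exact test, or site as a term in the Poisson model) will be reported beside the overall result. Choose one of the two methods before the data are examined.

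Add the same sentence, with referrals in place of implants, to Primary Objective #2 in section 11.1.

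Cost: one sentence in each place, one table and one further analysis for each endpoint, all on data already collected. The overall test is unchanged. The stratified estimate is somewhat less precise, because sites with SND subjects in only one phase add nothing to it. With about 63 SND subjects in all (21 + 42), it should be read as a check on the pooled result, not as a replacement for it.
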